4.2 Staging Criteria

Staging criteria are not applicable to this protocol.

5.0 ELIGIBILITY CRITERIA

Each of the criteria in the following section must be met in order for a patient to be considered eligible for registration. Use the spaces provided to confirm a patient's eligibility. For each criterion requiring test results and dates, please record this information on the Prestudy Form and submit to the Data Operations Center in Seattle (see [Section 14.0](#)). Any potential eligibility issues should be addressed to the Data Operations Center in Seattle at [name] or [contact] prior to registration.

In calculating days of tests and measurements, the day a test or measurement is done is considered Day 0. Therefore, if a test is done on a Monday, the Monday 4 weeks later would be considered Day 28. This allows for efficient patient scheduling without exceeding the guidelines. **If Day 28 or 42 falls on a weekend or holiday, the limit may be extended to the next working day.**

SWOG Patient No. _____

Patient's Initials (L, F, M) _____

5.1 Induction Registration (Step 1)

- _____ a. For patients registered to the relapsed/refractory cohort (Cohort 2), patients must have a previous morphologically confirmed diagnosis of acute myeloid leukemia (AML).

For patients registered to the MDS transformed to AML cohort (Cohort 1), patients must have a previous morphologically confirmed diagnosis of MDS/CMML. Patients may have received previous non-intensive therapy (e.g. azacitadine, decitabine, low-dose cytarabine (LDAC), lenalidomide) given for treatment of MDS/CMML (with up to 20% blasts). At the time of registration they must have a morphologically confirmed diagnosis of AML.

Note: This protocol uses the WHO diagnostic criteria for AML (see [Section 4.1](#)). Patients with acute promyelocytic leukemia (APL, FAB, M3) or blastic transformation of chronic myelogenous leukemia are not eligible.

- _____ b. Patients must NOT have received autologous or allogeneic stem cell transplantation.

Patients in the relapsed/refractory AML cohort (Cohort 2), must meet all of the following additional criteria:

1. Patient must have received at least one prior Induction chemotherapy regimen for their AML;
 - they may have received any type of chemotherapy
 - administration of hydroxyurea to control high WBC prior to, during, and after registration is permitted
2. Relapse or refractory disease must be documented by a bone marrow examination demonstrating > 5% blasts in the bone marrow not attributable to another cause;
3. Patient must NOT have received chemotherapy within 14 days prior to registration;

- _____ d. Primary refractory patients will be eligible if, on Day 14 of their previous chemotherapy regimen, they have significant residual disease. Patients who received only hypomethylating agent or low dose therapy for Induction are not considered primary refractory for purposes of this study and are not eligible.

- _____ e. Relapsed patients must have achieved a complete remission (CR) or CR with incomplete blood count recovery (CRi) lasting < 6 months with their last induction regimen.

SWOG Patient No. _____

Patient's Initials (L, F, M) _____

5.1 Induction Registration (Step 1) (contd.):

- _____ f. Patients must not have symptomatic congestive heart failure, coronary artery disease, cardiomyopathy, or uncontrolled arrhythmias. Either an echocardiogram or MUGA scan with an ejection fraction $\geq 45\%$ must be obtained within 28 days prior to registration, or within 14 days prior to registration if the patient has received anthracycline in the 28 day window. (Either method for measuring cardiac function is acceptable; however, the same scan must be used throughout treatment and follow-up to monitor the patient for cardiac toxicity.) If the patient has symptoms suggestive of ischemia or congestive heart failure after that cardiac evaluation was done, a repeat study must be obtained prior to registration.
- _____ f. Patients must have a serum creatinine < 2.0 mg/dl within 14 days prior to registration.
- _____ g. Patients must have a total bilirubin $\leq 2.0 \times$ Institutional Upper Limit of Normal (IULN) within 14 days prior to registration, unless the elevation is due primarily to elevated unconjugated hyperbilirubinemia secondary to Gilbert's syndrome or hemolysis and not to liver dysfunction.
- _____ h. Patients must have SGOT (AST) $\leq 3.0 \times$ IULN and SGPT (ALT) $\leq 3.0 \times$ IULN within 14 days prior to registration. Treatment may begin with SGOT/SGPT above those limits, if the abnormalities are thought to be due to the patient's leukemia.
- _____ i. Patients must have Zubrod performance status of 0-2 (see [Section 10.7](#)).
- _____ j. Patients must be ≥ 18 years of age.
- _____ k. Patients must not have clinical evidence of leptomeningeal disease (a spinal tap does not need to be performed).
- _____ l. Patients who are known to be HIV+ may be eligible providing they meet all of the following additional criteria within 28 days prior to registration:
 - 1. Patient must have no history of AIDS defining events.
 - 2. CD4 cells $\geq 500/\text{mm}^3$.
 - 3. Viral load of < 50 copies HIV mRNA/ mm^3 if on cART or $< 25,000$ copies HIV mRNA if not on cART.
 - 4. No zidovudine or stavudine as part of cART.

Patients who are HIV+ and do not meet all of these criteria will not be eligible for this study.

SWOG Patient No. _____

Patient's Initials (L, F, M) _____

5.1 Induction Registration (Step 1) (contd.):

- _____ m. Patients with prior malignancy (other than AML and MDS/CMML) are eligible. However, the patient must be in remission from the prior malignancy and have completed all chemotherapy and radiotherapy at least 6 months prior to registration. Except for AML and MDS treatment, all treatment related toxicities must have been resolved.

NOTE: For patients with prior history of malignancy who have received anthracyclines or mediastinal/pericardial radiation in the past, the risk versus benefit of therapy should be weighed, particularly in the setting of receiving consolidation therapy.

- _____ n. Patients must not have a systemic fungal, bacterial, viral or other infection that is not controlled (defined as exhibiting ongoing signs/symptoms related to the infection and without improvement, despite appropriate antibiotics or other treatment).
- _____ o. Pretreatment cytogenetics must be performed on all patients. Collection of pretreatment specimens must be completed within 28 days prior to registration to **S0919**. Specimens must be submitted to the site's preferred cytogenetics laboratory (see [Section 15.1](#)).
- _____ p. Women of reproductive potential must have a negative pregnancy test within 14 days prior to registration. Patients must not be pregnant or nursing because of the teratogenic potential of the drugs used in this study. Women/men of reproductive potential must have agreed to use an effective contraceptive method.
- _____ q. Patients must have complete history and physical examination within 28 days prior to registration.
- _____ r. All patients must be informed of the investigational nature of this study and must sign and give written informed consent in accordance with institutional and federal guidelines.
- _____ s. As a part of the OPEN registration process (see Section 13.3 for OPEN access instructions) the treating institution's identity is provided in order to ensure that the current (within 365 days) date of institutional review board approval for this study has been entered in the system.

Each of the criteria in the following section must be met in order for a patient to be considered eligible for registration. Use the spaces provided to confirm a patient's eligibility. For each criterion requiring test results and dates, please record this information on the **S0919** Consolidation Eligibility Form and submit to the Data Operations Center in Seattle (see [Section 14.0](#)). Any potential eligibility issues should be addressed to the Data Operations Center in Seattle at [name] or [contact] prior to registration.

SWOG Patient No. _____

Patient's Initials (L, F, M) _____

5.2 Consolidation Registration (Step 2)

After completing Induction therapy, patients may be registered for Consolidation therapy **provided** that they were eligible for the initial registration and **satisfy** the following additional criteria at the time of Consolidation registration:

- _____ a. Patients must have achieved CR as defined in [Section 10.1c](#). Patients who achieved only CRi or PR, and patients who relapse from CR ([Section 10.3](#)) before this registration are not eligible.
- _____ b. Patients must not have symptomatic congestive heart failure, coronary artery disease, cardiomyopathy, or uncontrolled arrhythmias. Either an echocardiogram or MUGA scan with an ejection fraction $\geq 45\%$ must be obtained within 14 days prior to registration. (The same scan that was used during induction registration must be used for consolidation registration.) The ejection fraction must not have dropped $\geq 10\%$ from the baseline ejection fraction. If patient has had symptoms suggestive of ischemia or congestive heart failure after that cardiac evaluation was done, a repeat study must be obtained prior to registration.
- _____ c. Patients must have a serum creatinine < 2.0 mg/dl within 14 days prior to registration.
- _____ d. Patients must have a total bilirubin $\leq 2.0 \times$ Institutional Upper Limit of Normal (IULN) within 14 days prior to registration, unless the elevation is due primarily to elevated unconjugated hyperbilirubinemia secondary to Gilbert's syndrome or hemolysis and not to liver dysfunction.
- _____ e. Patients must have SGOT (AST) $\leq 3.0 \times$ IULN and SGPT (ALT) $\leq 3.0 \times$ IULN within 14 days prior to registration.
- _____ f. Patients must have Zubrod performance status of 0-2 (see **Section 10.8**).
- _____ g. Patients must not have a systemic fungal, bacterial, viral or other infection that is not controlled (defined as exhibiting ongoing signs/symptoms related to the infection and without improvement, despite appropriate antibiotics or other treatment).
- _____ h. Patients must have ANC $\geq 1,000/\text{mcl}$ and platelets $\geq 100,000/\text{mcl}$ within 7 days prior to registration.
- _____ i. Patients must be registered to Consolidation therapy (Step 2) within 60 days of beginning Induction therapy (with Day 1 being the start of Induction).

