9.0 STUDY CALENDARS

9.1 Remission Induction Therapy

REQUIRED STUDIES	Pre	D	D	D	D	D	D	D	Wk	Wk	Wk	Wk	Wk	Wk	Relapse	Follow Up
	Study	1	2	3	4	5	6	7	2	3	4	5	6	7		
PHYSICAL																
History & Physical Exam #	X	1x/wk							X	X	X	X	X	X		X
Performance Status	X															
Toxicity Notation	X	1x/wk							X	X	X	X	X	X		X
Neurotoxicity evaluation ¶	X				X	X	X	X								
Leptomeningeal disease evaluation	X															
LABORATORY STUDIES																
CBC, Diff, Platelets Δ	X	2x/wk							2x/wk	2x/wk	2x/wk	X	X	X		X
PT, PTT ✓	X	1x/wk							X	X	X					
Serum creatinine α	X	X			X	X	X	X	2x/wk	2x/wk	2x/wk	X	X	X		
Total bilirubin α	X	X			X	X	X	X	2x/wk	2x/wk	2x/wk	X	X	X		
SGOT and SGPT α	X	X			X	X	X	X	2x/wk	2x/wk	2x/wk	X	X	X		
Disease Assessment/BMAsp/Bx	X								Xd							X
Pregnancy test β	X															
X-RAYS AND SCANS																
Chest X-Ray ✓	X															
EKG ✓	X															
MUGA or ECHO Ω	X															
TREATMENT (see Section 7.0)																
Pravastatin		X	X	X	X	X	X	X	Day 8							
Idarubicin					X	X	X									
AraC					X	X	X	X								

Continued on next page
Click here for [Footnotes](#):

Footnotes for Calendar:

- # Complete history and physical exam should be performed within 28 days prior to registration and at least once a week until Day 45.
- Δ CBC/diff/plts should be performed at least twice weekly until Day 28 and then at least once weekly until Day 45. Differential is not required if WBC < 0.5.
- α To be performed daily prior to chemotherapy administration on Day 1 and 4-7, then at least twice weekly until Day 28 and then at least once weekly until Day 45.
- √ To be performed as part of good medical practice. Results do not determine eligibility.
- Ω Either MUGA or ECHO may be performed at baseline. The same test should be used throughout protocol therapy and follow-up.
- ¥ To be performed prior to each dose of AraC ([see Section 7.3](#)).
As determined by clinical evaluation. Spinal tap does not need to be performed (see [Section 5.1k](#)).
- β Women of reproductive potential must have a negative pregnancy test within 14 days prior to registration (see [Section 5.1p](#)).
- ¶ Follow up exams will be performed monthly for the first year, every three months for the second and third years, and every 6 months for the fourth and fifth years. Exams will include at a minimum history and physical, toxicity notation, and CBC, Diff, Plts, with additional testing at the discretion of the treating physician.

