9.2 Consolidation Therapy

¶

REQUIRED STUDIES	Pre Cycle 1	D 1	D 2	D 3	D 4	D 5	D 6	D 7	Wk 2	Wk 3	Wk 4	Wk 5	Pre Cycle 2	D 1	D 2	D 3	D 4	D 5	D 6	D 7	Wk 2	Wk 3	Wk 4	Wk 5	Relapse	FU	
PHYSICAL																											
History & Physical Exam # Σ	X	1x/wk							X	X	X	X	X	1x/wk							X	X	X	X			X
Performance Status #	X												X														
Toxicity Notation Σ		1x/wk							X	X	X	X	X	1x/wk							X	X	X	X			X
Neurotoxicity evaluation \pounds					X	X											X	X									
LABORATORY STUDIES																											
CBC, Diff, Platelets Δ	X	2x/wk							2x/wk	2x/wk	2x/wk	X	X	2x/wk							2x/Wk	2x/wk	2x/wk	X		X	
PT, PTT \checkmark	X																										
Serum creatinine α	X	X			X	X			2x/wk	2x/wk	2x/wk	X	X			X			X		2x/Wk	2x/wk	2x/wk	X			
Total bilirubin α	X	X			X	X			2x/wk	2x/wk	2x/wk	X	X			X			X		2x/Wk	2x/wk	2x/wk	X			
SGOT and SGPT α	X	X			X	X			2x/wk	2x/wk	2x/wk	X	X			X			X		2x/wk	2x/wk	2x/wk	X			
Disease Assessment/BM Asp/Bx	X \pounds																								X		
X-RAYS AND SCANS																											
MUGA or ECHO Ω	X												X														
TREATMENT (see Section 7.0)																											
Pravastatin		X	X	X	X	X	X							X	X	X	X	X	X								
Idarubicin					X	X											X	X									
AraC					X	X											X	X									

Continued on next page.
Click here for [Footnotes](#):

Footnotes for Calendar 9.2

- # To be performed within 28 days prior to registration and prior to each Consolidation Cycle.
- Σ To be performed weekly until hematologic complete recovery.
- Δ To be performed prior to Consolidation registration (see [Section 5.2](#)), at least twice weekly until Day 28 and then at least once weekly until Day 35 for each consolidation cycle. Differential is not required if WBC < 0.5.
- α To be performed on Day 1, 4 and 5 then at least twice weekly until Day 28 of each Consolidation cycle, and then at least once weekly until Day 35 of each Consolidation cycle. Dosing may be administered based on the values collected at each scheduled assessment, providing the values are within those allowable in [Sections 5.2](#) and [8.2d](#). If the values are elevated, therapy should be held/adjusted (see [Sections 5.2](#) and [8.2d](#)).
- √ To be performed as part of good medical practice. Results do not determine eligibility
- Ω To be performed prior to each Cycle of Consolidation therapy. The same test as used during baseline assessment must be used.
- ¥ To be performed prior to each dose of AraC (see [Section 7.4](#)).

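### The pregnancy exclusion and negative test apply only at Step 1; the plan as available repeats neither before the two Consolidation cycles of the same drugs

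*Combined protocol and SAP*

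**What the plan says.** At Step 1, section 5.1p sets three conditions. It states "Patients must not be pregnant or nursing because of the teratogenic potential of the drugs used in this study". It requires a negative test in the 14 days before registration for women of reproductive potential. It also adds "Women/men of reproductive potential must have agreed to use an effective contraceptive method". The Induction calendar (9.1) has a pregnancy-test row, marked in the pre-study column only, with the footnote "Women of reproductive potential must have a negative pregnancy test within 14 days prior to registration".

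At Step 2, section 5.2 requires that patients were eligible at initial registration and satisfy "the following additional criteria at the time of Consolidation registration". Items a to i cover remission, cardiac function, creatinine, bilirubin, transaminases, performance status, infection, blood counts and the 60-day limit. Item a rules out "Patients who achieved only CRi or PR, and patients who relapse from CR", so only patients in full CR go on.

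Section 7.4 allows two cycles of pravastatin, idarubicin and AraC. Before cycle 2 it asks for continued remission, neutrophil and platelet thresholds, and a cardiac scan. Calendar 9.2 has no pregnancy-test row. Its footnotes schedule the history and physical examination as "To be performed within 28 days prior to registration and prior to each Consolidation Cycle" and "To be performed weekly until hematologic complete recovery". Calendar 9.1 asks for the same examination at least weekly to Day 45.

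Three other places deal with pregnancy or could apply to it. Section 3.3b recommends stopping pravastatin once a pregnancy is recognized. Section 16.1f requires expedited reporting. Section 7.8 lists reasons for removal from treatment; pregnancy is not named among them.

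**The concern.** The reason section 5.1p gives for its exclusion is the drugs themselves, and those drugs are given again in Consolidation. Pregnancy status can change between the two steps, as can the cardiac, renal, hepatic and infection findings that section 5.2 does check again. The clause about initial eligibility looks back to Step 1 and says nothing about status on the day of Step 2 registration. Cycle 2 has no registration of its own, so nothing in the eligibility text reaches it.

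What is at stake is fetal harm. The protocol's drug sections say that AraC can cause it (3.1b). They report that idarubicin was embryotoxic and teratogenic in the rat, though not teratogenic in the rabbit and without conclusive human information (3.2c). They say that the safety of pravastatin in pregnancy has not been established (3.3b). A site that follows the plan exactly could start either Consolidation cycle in a woman with an unrecognized pregnancy.

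**Working it through.** The documents state no test age, so there is no figure of the plan's own to reproduce. The age follows from the stated windows.

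**Inputs**

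- a, test to Step 1 registration: 0 to 14 days (5.1p).
- b, registration to start of Induction: 0 to 7 working days (13.1). With no holiday, seven working days are 9 calendar days for a Monday-Wednesday registration and 11 for Thursday-Friday.
- c, start of Induction to cycle 1: Day 30 to Day 60, with the start of Induction as Day 1 (7.4), so 29 to 59 days later.
- d, cycle 1 to cycle 2: 30 to 60 days (7.4, which gives no Day 1 note here).

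**Age of the only required test** = a + b + c at cycle 1 Day 1, and a + b + c + d at cycle 2 Day 1.

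| | Shortest | Longest under ordinary windows |
|---|---|---|
| Cycle 1 Day 1 | 0 + 0 + 29 = 29 | 14 + 9 + 59 = 82 to 14 + 11 + 59 = 84 |
| Cycle 2 Day 1 | 29 + 30 = 59 | 82 + 60 = 142 to 84 + 60 = 144 |

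An illustrative mid-window patient (test 7 days before registration, start 3 days later, cycle 1 on Day 45, cycle 2 after 45 days) is at 7 + 3 + 44 = 54 days and 54 + 45 = 99 days.

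**Sensitivity**

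- Reading the cycle 1 window as elapsed days adds one day throughout: 30 to 83-85, and 60 to 143-145.
- Reading the cycle 2 window as day numbers takes one day off: 58 to 141-143.
- One holiday can stretch b to 12 days, giving maxima of 14 + 12 + 59 = 85 and 85 + 60 = 145.
- If an 8-day hold under section 8.3 extends the windows, one hold in Induction gives 82 + 8 = 90 to 84 + 8 = 92 at cycle 1. A second hold in cycle 1 gives 90 + 60 + 8 = 158 to 92 + 60 + 8 = 160 at cycle 2.

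The maxima in the table are therefore not absolute ceilings, although reaching them already needs every window at its limit.

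**How many women would be tested.** The documents give neither a CR/CRi split nor an age and sex mix. I assume a true response rate (CR plus CRi) between the design's 20% and 40%, that 50-80% of responders are in CR, that 5-25% of these are women of reproductive potential, and that every CR patient receives both cycles.

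- CR patients: 74 × 0.20 × 0.50 = 7.4 to 74 × 0.40 × 0.80 = 23.7.
- Women tested: 7.4 × 0.05 = 0.4 to 23.7 × 0.25 = 5.9. If no responder were CRi, the upper figure would be 74 × 0.40 × 0.25 = 7.4.
- Tests, at two per woman: about 0.7 to 11.8.

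These are women tested, not pregnancies.

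**After the fix.** With a test within 14 days before Step 2 registration, and the section 13.1 limit applied to that registration, the longest age at cycle 1 is 14 + 9 = 23 to 14 + 11 = 25 days. Without a further test it would reach 23 + 60 = 83 to 25 + 60 = 85 days at cycle 2. With one, the longest age there is 14 days.

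**The case against.** The strongest reply is that this is a deliberate, partial re-check. Section 5.2 does not repeat the leptomeningeal (5.1k) or HIV (5.1l) criteria either. Patients of reproductive potential have agreed to contraception. They are examined at least weekly to Day 45 of Induction, then before each Consolidation cycle and weekly, so the long test ages fall in a period of close clinical contact. Sites may test at their discretion. A recognized pregnancy is not ignored, given sections 3.3b and 16.1f, and an investigator might use the unacceptable-toxicity ground in section 7.8d. Test age is not a measure of risk, and the documents give no probability of pregnancy. The calendars also defer to external SWOG guidelines, the drug sections defer to package inserts, and the consent pages are not in the text. Any of these might ask for more.

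Much of this stands. It makes the point small and keeps it from being a contradiction in the plan. It does not remove it. The leptomeningeal and HIV criteria are not justified by the teratogenicity of the drugs, as the pregnancy exclusion is. An examination or a contraception agreement is not a test, and section 5.1p asks for a test in addition to the agreement. Sections 3.3b and 16.1f act only once a pregnancy is known. Pregnancy also fits poorly under toxicity.

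**Conclusion.** The omission is confirmed for the text available: nothing in sections 5.2 or 7.4, or in calendar 9.2, repeats the section 5.1p exclusion or test before either Consolidation cycle. The required test is at least 29 and 59 days old at the two cycle starts, about twice and four times the protocol's own 14-day window. It can be about 82-84 and 142-144 days old with every window at its limit, without holidays or holds. Under the stated assumptions about 0 to 6 of 74 patients would be tested, and there may be no pregnancy among them. Type I error, power and the primary analysis are unaffected. This is a cheap improvement to patient safety, of low priority.

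A reader might infer that a pregnancy would be exposed a second time. That holds only if it already existed during Induction; one conceived later would be exposed for the first time. A reader might also infer that the plan has no safeguard or no guidance on pregnancy. The documents do not support that, given the contraception agreement, the examinations, and sections 3.3b and 16.1f. Nor do they show that no test was ever required, because the sources that could not be checked might require one.

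**What to change.** 1. Add the section 5.1p pregnancy and nursing criterion to section 5.2, with a negative test within 14 days before Step 2 registration for women of reproductive potential.
2. Add to the section 7.4 conditions for starting cycle 2 a negative test within 14 days before cycle 2 Day 1. State in section 7.8 that a patient with a confirmed pregnancy receives no further protocol treatment. A calendar row alone would leave a positive result before cycle 2 without a stated consequence.
3. Add a pregnancy-test row to the Pre Cycle 1 and Pre Cycle 2 columns of calendar 9.2.

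The cost is a few lines of text, one calendar row and one field on the form for Step 2 eligibility. It also means about 1 to 12 routine laboratory tests in all, under the assumptions above, at visits where blood is already drawn. The downside is that a positive result would need confirmation and could delay a cycle that has to start within its 60-day limit.
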